# New User Protocol for Diabetes, Insulin and Malignancies Study (DIMSum) 23Jan2012

# 1. Background

There have been several reports in the scientific literature purporting to show a relationship between the use of insulin to treat diabetes and the development of cancer. More recently, four publications appeared in the journal Diabetologia regarding the possibility that the long-acting insulin analogue glargine (Lantus) was specifically associated with an increased overall cancer risk compared with all other insulins. Overall these results have inconsistent findings across analyses, a small number of cancer cases, short periods of observation, and some methodological flaws.

# 2. Objective of the Study

The objective of the study is to investigate the causal effect of initiating glargine compared with human NPH insulin on the risk of cancer in people with diabetes using population-based databases.

#### 3. Study Organization

The study is administered and coordinated by investigators at the University of North Carolina at Chapel Hill (UNC-CH). The principal investigator of the study is [name], PhD, who is a Professor of Medicine, Chief of the Division of Endocrinology, and Executive Associate Dean for Clinical Research at the UNC School of Medicine. [name] is joined by [name], Professor of Biostatistics, and Investigator at the Collaborative Studies Coordinating Center, and [name], MPH, PhD, Professor of Epidemiology, head of the pharmacoepidemiology program and Director of the UNC Center of Excellence in Pharmacoepidemiology and Public Health.

The UNC-CH coordinating center supports the work of U.S. based study sites that have comprehensive, longitudinal databases of diabetic patients. UNC-CH's role on the project is to coordinate development of a common study protocol, ensure proper ascertainment of study subjects and suitability of data to conduct a meta-analysis, formulate ancillary research questions, and ensure the proper analysis and reporting of the study results.

Advisors to the study include representatives appointed by the American Cancer Society and the American Diabetes Association. The study is funded by a grant to UNC-CH from the company sanofi-aventis. UNC-CH funds collaborators from the study sites. Sanofi-aventis will have no role in formulating the final protocol, data analysis, interpretation of results, or manuscript(s) development for publication. The study is performed under a common protocol across the US study sites.

#### 4. Data Sources

# i) Ochsner Health System in Louisiana

A decade ago, the Chief Information Officer at Ochsner facilitated the development of the diabetes registry that now includes 30,000 patients. The registry has information from the institutional electronic medical record and also contains claims, laboratory, pharmacy and hospital data. Most of the diabetes patients in the registry have over five years of follow-up. Ochsner also has a cancer registry which will be linked to the diabetes registry for the analysis. [name], is PI of the Ochsner site.

# ii) Partners HealthCare System in Massachusetts

The Massachusetts General Hospital Primary Care Practice-Based Research Network (PBRN) consists of a network of outpatient practices in eastern Massachusetts affiliated with Massachusetts General Hospital (MGH) and the Partners HealthCare System (PHS). The practices include three hospital-affiliated academic practices, four community health centers, and six private practice offices, together serving a wide range of communities and patient populations. PBRN practices share a common electronic health record containing all clinical and utilization data for each patient. Approximately 155,000 patients receive regular care from a primary care physician in the network. Patients with diabetes are identified using a previously validated algorithm. This diabetes cohort has about 15,700 patients (primarily type 2) who are under active care at MGH by a known primary provider. All prevalent and incident cancers of interest are identified by linkage with the Massachusetts General Hospital tumor registry. [name], is PI of the Partners site.

### iii) MedAssurant

MedAssurant is a Maryland medical informatics company that provides analytic services to more than 200 health care organizations across the country with the goal of identifying opportunities to improve quality and outcomes of care and reduce healthcare costs. MedAssurant has built a large healthcare database, the MORE2 Registry, that contains data for over 76 million patients, 295,000 physicians, and 185,000 clinical facilities. The registry allows for tracking patients over time and across health plans (as long as data are available from all of the patient's health plans) and thus the usual follow-up time for patients in the MedAssurant database is longer than the follow-up time in databases relying on a single insurer. [name], is PI of the MedAssurant site.

# iv) Solucia

Solucia is another medical informatics company that provides actuarial services to insurers, employers and health care providers. Their database contains data for over 215,000 diabetics with an average of two years of follow-up. They are located in Connecticut and [name] is the PI of the Solucia site.

Though the sample sizes of the MedAssurant database and the Solucia database are substantially greater than that of the additional sites (Partners and Ochsner), the latter sites will provide opportunities to explore the issue of channeling of prescriptions to glargine or NPH insulin based on important potential confounders such as BMI and type of diabetes, discussed elsewhere.

# 5. Analysis Plan

The analysis strategy corresponds to a new user cohort design in which subjects enter the cohort at time of first use of insulin (glargine or NPH; see Section 5.2 for definition of first use), and baseline information is ascertained over a fixed period prior to first use. New user designs have been increasingly embraced by pharmaco-epidemiologists since 2003, when Ray published an article which argued that the new user design can reduce the potential for many of the biases likely present in a prevalent user design. One source of bias in a prevalent user design is that prevalent users of a given treatment are not a random sample of all the patients who began using this treatment at a particular time in the past. For example, intolerance to a treatment may lead to differential dropout, which results in a survivor cohort that is more likely to do well with the therapy (i.e. the "healthy user" effect). This is likely the reason that observational studies did not demonstrate an increased cardiovascular risk associated with hormone replacement therapy, whereas randomized trials did uncover this effect. It may also be the reason that researchers were led to believe that third generation oral contraceptives were associated with a higher rate of venous thromboembolism compared with second generation oral contraceptives.

The magnitude of the risks and benefits of drugs often vary over time after the start of treatment, which introduces bias into a prevalent user design; a new user design helps to control this bias. Another difficulty in the analysis of prevalent user designs stems from the fact that disease risk factors can be affected by the treatment itself. In a new user design, this difficulty is addressed because potential confounders can be measured prior to treatment initiation. Although the benefits of the new user design are well understood and

attractive, such designs are often not employed because of the logistical complexities of identifying new users and because of the loss of sample size and thus statistical power compared with a prevalent user design.

Data from Ochsner Health System and Partners HealthCare System will be extracted and transferred to UNC-CH for analysis. The Solucia database will also be analyzed by UNC-CH and the analysis of the MedAssurant database will be performed at MedAssurant.

As a first step in the analysis, UNC-CH used data from Partners HealthCare System to determine the extent of channeling based on BMI. Based on the data available from Partners as of May 2011, channeling associated with BMI appears to be minimal; thus, it is feasible to include claims data in this project. Although BMI is not available in claims data, the inclusion of the MedAssurant claims dataset ensures sufficient power for the new user analysis.

The respective analysis groups (UNC-CH and MedAssurant) will perform the new user analysis described in the subsections that follow. The site-specific results from the larger databases will then be combined in a meta-analysis of the hazard ratios of glargine versus NPH for each of the four cancer endpoints. Estimated hazard ratios from each of the data sources will be combined in the meta-analysis by inverse variance weighting. Site-specific results will be compared to examine site-to-site differences in hazard ratios (heterogeneity).

# 5.1 Study Population

For the analysis of data from Partners HealthCare System and Ochsner, individuals from their diabetes registries will be eligible to enter the new user cohort on January 1, 2005 (approximately) or later at the time of their first eligible prescription of either insulin glargine or NPH insulin. Diabetes will be defined in the MedAssurant database by having at least 1 diagnostic code (ICD-9 code 250.x) for diabetes during the 18 months prior to or on the date of the first eligible prescription of glargine or NPH insulin. The earliest date when individuals in the MedAssurant database will enter the new user cohort is July 1, 2004. Individuals must have at least 19 months of continuous membership and pharmacy benefits prior to new user cohort entry; if membership is not well defined, a prescription is required in each of four 6-month periods prior to the first eligible prescription. The cohort will be restricted to adults (aged 18 years and older), since the most common cancers rarely occur in children.

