#### Cohort exclusion criteria

Individuals will be excluded from the cohort for the following:

- Less than 18 years of age.
- Prevalent cancer. Patients with evidence of a history of any cancer (except non-melanoma skin cancer) at cohort entry will be excluded.
- Use of insulin other than 1 prescription for a short-acting insulin in the 19 months prior to the first cohort defining insulin. A period of 19 months is used to allow for an estimated one month supply from any previous insulin prescription, a 6 month grace period, and a 12 month wash-out period.

For the primary new user analysis, evidence of prior cancer or prior surgeries must occur within the 19 months prior to the first prescription for a long-acting insulin in order for the patient to be excluded from the relevant analyses.

In addition, patients may be excluded from specific analyses as described below:

- For breast cancer, women with prophylactic unilateral or bilateral mastectomy at cohort entry will be excluded from the breast cancer analysis.

- For colon cancer, men and women with evidence of complete or subtotal surgical prophylactic removal of the colon will be excluded from the colon cancer analysis.
- For prostate cancer, men with a partial or complete prostatectomy for any reason will be excluded from the prostate cancer analysis.

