### 5.2 Exposures of Interest

The analysis will be based on new users of insulin glargine and new users of human NPH insulin. Patients who use premixed NPH insulin will be included with NPH insulin users in the primary analysis.

In the MedAssurant analyses, the cohorts will be defined as of the second prescription of a long-acting insulin following the first eligible prescription (see Section 5.1 Study Population). The second prescription must occur within 6 months after the first eligible prescription and patients must receive the same type of long-acting insulin (glargine or NPH) at the first and second prescription. Patients with discrepant insulin prescriptions between their 1st and 2nd prescriptions will not be included in the primary analysis but they will be identified for possible inclusion in secondary analyses. In the Ochsner and Partners HealthCare analyses, only one record indicating the start of glargine or NPH will be required to enter the cohort since the electronic medical record databases do not keep a record of every subsequent prescription.

At the first eligible prescription following the cohort entry date, we will determine whether this is an instance of new use based on whether the patient had a prescription for insulin during the 19 months prior to the first eligible script. A 19-month evaluation period ensures that a patient has at least a 12-month insulin-free period prior to entering the new user cohort as it includes time for a 1 month supply following any prior insulin prescription plus a 6-month grace period plus a 12-month washout period. Note that a patient must have at least 19 months of medication data prior to their first prescription for glargine or NPH in order to be evaluated for the new user cohort; for patients with more than 19 months of data, only the latest 19 months of data will be used. Patients without any prescription for insulin during the 19 months prior to the first eligible script, or with only one prescription for a short-acting insulin during this time period, will be considered new users and will be included in the primary analysis.

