#### 5.4 Covariates

All covariates are defined based on available information within the 12-month period prior to and including the date of the first long-acting insulin prescription. It is important that this time is constant irrespective of the availability of additional data.

The minimum set of covariates includes age, gender, cohort entry date, co-morbidities (e.g., COPD as proxy for smoking), co-medication (including but not limited to other antidiabetic medications), health care system use (number of in- and outpatient encounters, days hospitalized), and screening behavior (especially cancer screening, see table). If available, smoking status, family history of cancer (overall and specific cancers, if available), body mass index, and duration of diabetes are also covariates of interest.

Potential confounders for specific types of cancers include use of hormone therapy and use of oral contraceptives.

Covariates by category are as follows:

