# 5.5 Baseline and follow-up (time at risk)

Baseline is defined as the 12-month time period up to and including the date of first prescription of glargine or NPH for new users; all covariates will be assessed based on data from this 12-month period. The start of follow-up for Ochsner and Partners HealthCare System patients will be the date of the first prescription. The start of follow-up for new users in the MedAssurant database will be defined for each cohort member as the date of the second prescription for glargine or the glargine comparator insulin. Note that the first and second prescriptions can be for different insulins as long as both insulins reside within the same group (i.e. glargine or NPH,).

The use of the second prescription allows us to remove patients who filled a prescription but were minimally or never exposed to the insulin products of interest. The potential for this kind of exposure misclassification is much smaller given the dispensing of a second prescription. The use of the second prescription as the start of follow-up results in the potential for changes in prescribed type of insulin (see above), covariates, and exclusion criteria. We will ignore changes in covariates because such changes may already be affected by the first prescription. Patients developing cancer between the first and second prescription will be flagged, enumerated, and excluded from the primary analysis.

Follow-up will generally end at: (1) diagnosis of any cancer (except non-melanoma skin cancer) for both overall cancer and specific subgroups, (2) death, (3) a gap of greater than 6 months in either membership or prescription benefits (if membership is not well defined, if no diagnostic code OR no prescription for

more than 6 months during follow-up; a final determination will be made following a review of the data), or (4) the end of the study (date to be determined with individual sites); whichever comes first. In addition, for the analyses on breast, colon, and prostate cancer risk, patient follow-up will be censored when the target organ is removed for a non-cancer related reason.

- For the breast cancer analysis, complete bilateral mastectomy;
- For the colon cancer analysis, removal of colon;
- For the prostate cancer analysis, complete prostatectomy, when done for reasons not related to prostate cancer.

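### The fallback look-back rule in section 5.1 allows almost 12 months between prescriptions, although section 5.5 ends observation of such patients after more than 6 months

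*Protocol*

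**What the plan says.** **Entry.** The main rule in section 5.1 is strict: "Individuals must have at least 19 months of continuous membership and pharmacy benefits prior to new user cohort entry". The fallback follows in the same sentence: "if membership is not well defined, a prescription is required in each of four 6-month periods prior to the first eligible prescription". It sets no largest interval between prescriptions and asks for no medical encounter per period. The only diagnosis code needed for entry in MedAssurant is one diabetes code in the 18 months up to the first eligible prescription.

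**Follow-up.** Item (3) in section 5.5 ends follow-up at a gap of over six months in membership or prescription benefits. Its own fallback reads "if membership is not well defined, if no diagnostic code OR no prescription for" more than six months. A note that the final decision awaits a look at the data is attached to this follow-up rule, not to the entry rule.

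**What rests on the look-back.**
- Insulin-free time (section 5.2): "A 19-month evaluation period ensures that a patient has at least a 12-month insulin-free period prior to entering the new user cohort". The 19 months are built from "an estimated one month supply from any previous insulin prescription, a 6 month grace period, and a 12 month wash-out period". Section 5.2 also says "a patient must have at least 19 months of medication data prior to their first prescription for glargine or NPH", without saying that the data must be free of gaps.
- Cancer and surgery history (cohort exclusion criteria): "evidence of prior cancer or prior surgeries must occur within the 19 months prior to the first prescription for a long-acting insulin".
- Covariates (section 5.4): "All covariates are defined based on available information within the 12-month period prior to and including the date of the first long-acting insulin prescription".

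Appendix A starts the washout clock at the start of continuous enrollment and gives no version for patients admitted through the fallback.

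**The concern.** All three windows assume that the patient was observable. In claims data an event with no record is read as an event that did not happen. If the entry rule admits a long silent interval, the absence of insulin, cancer or comorbidity in that interval may reflect missing data. Section 4 gives a concrete route: MedAssurant can follow a patient across plans only while every one of that patient's plans supplies data. Time in a plan that does not contribute leaves just such a gap.

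At stake are the new-user status of some patients, their cancer-free status at entry, and the completeness of the propensity score covariates. The protocol also applies two different standards of observation to the same kind of patient, one before entry and a tighter one after it.

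**Working it through.** **1. The plan's own figure.** 1 month of supply + 6 months of grace + 12 months of washout = 19 months. The stated window reproduces.

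**2. Largest accepted interval.** Assume four consecutive periods of length P days, counted back from the first eligible prescription. A fill on the first day of one period and the next on the last day of the following period satisfies the rule. The interval is 2P − 1 days:
- P = 180: 359 days (11.8 months)
- P = 182: 363 days (11.9 months)
- P = 183: 365 days (12.0 months)

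The limit in section 5.5 is six months, so the ratio is about 2 (365/183).

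**3. An admissible extreme.** With P = 183, fills 1, 366, 367 and 732 days before the index prescription qualify. The intervals are 365, 1 and 365 days. The 365-day covariate window then holds one earlier fill, on the day before index. The 19-month window (578 days) holds three. If each fill is assumed to supply 30 days, 334 of 365 and 545 of 578 days show no drug coverage. With 90 days the figures are 274 and 485.

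**4. How often the rule lets a gap through (illustration).** Assume continuous fills apart from one gap of L months, with its start uniform over the 24 − L possible months. The rule rejects only a gap that contains a whole period. That excludes start times of total length 2(L − 6).
- Accepted, gap anywhere in the 24 months: 1 − 2(L − 6)/(24 − L).
- Accepted with more than 6 months of the gap inside the 19-month window: the start must also be later than month 11 − L of the 24. The share is [(24 − L) − (11 − L) − 2(L − 6)]/(24 − L) = (25 − 2L)/(24 − L).

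| L (months) | Anywhere in 24 months | More than 6 months inside the 19 |
|---|---|---|
| 7 | 15/17 = 88% | 11/17 = 65% |
| 8 | 12/16 = 75% | 9/16 = 56% |
| 9 | 9/15 = 60% | 7/15 = 47% |
| 10 | 6/14 = 43% | 5/14 = 36% |
| 11 | 3/13 = 23% | 3/13 = 23% |

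The right-hand column is the relevant one for washout and cancer history.

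**5. Sparse fillers (upper illustration).** With exactly one fill per period at a uniform date, an interval exceeds P whenever a fill falls later in its period than the preceding fill did in its own. No interval does so with probability 1/4! = 1/24, so 23/24 = 96% of admitted patients have at least one interval over six months. By simulation, 39% have one over 270 days and 19% one over 300 days. Patients who fill often would show far fewer.

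**6. What the other rules still catch.** A single gap of under 12 months leaves at least 19 − 12 = 7 months of the look-back outside it. Insulin seen there, beyond one short-acting prescription, excludes the patient, and so does cancer seen there. Two gaps, as in step 3, leave less.

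**The case against.** The strongest reply has four parts.

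- **No fill is not the same as no observation.** A patient without prescriptions may still generate visits and diagnosis codes. This stands: information in the gap can be missed, not must be.
- **Existing safeguards.** A reader might infer that continuing insulin users, or patients under cancer care, generally pass as new and cancer-free. The documents do not support that. Long-standing insulin use would usually show in the observed part of the 19 months. In claims data, follow-up starts at the second prescription and cancers arising between the first and second are excluded. Appendix C delays the start of follow-up by 6 to 24 months. This largely stands, but none of these measures restores missing washout or covariates, and no Appendix C analysis varies the look-back rule.
- **The benchmark is provisional and not identical.** Section 5.5 names diagnostic codes as well as prescriptions and leaves the final decision open. Read literally, either absence alone ends follow-up, so a prescription gap is enough. If both absences were meant, a prescription-only cap at entry would be somewhat stricter than follow-up. In either case the two rules need reconciling.
- **It is a contingency.** Continuous membership is the governing rule, and nothing shows how often, or in which databases, the fallback applies. This stands and limits the importance of the point.

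**Conclusion.** The inconsistency is real. Section 5.1 accepts up to about 12 months between prescriptions where section 5.5 treats more than six months of silence as the end of observation. The 12 insulin-free months are therefore not assured for patients admitted through the fallback, and their covariate window can be nearly empty of fills.

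The patients mainly at risk of misclassification are those whose insulin or cancer first arises inside the gap and is seen neither before the index prescription nor, for cancer in claims data, between the first and second prescriptions. Their number cannot be derived, because the protocol does not say how many patients lack well-defined membership. Nothing in it shows a difference between glargine and NPH users, so the direction of any bias in the hazard ratio is unknown.

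The percentages under the calculation are conditional on assumed gap patterns. A reader might take them as shares of the cohort; they are not. The conclusion rests on the four periods being consecutive and counted back from the first eligible prescription, which is the natural reading. This is a cheap improvement to an eligibility rule and does not show that the results would be wrong.

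**What to change.** Keep the four-period, 24-month requirement in section 5.1 and add one sentence, consistent with item (3) of section 5.5:

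*In addition, when membership is not well defined, no interval of more than 6 months without a prescription may overlap the 19 months up to the first eligible prescription; an interval that began before those 19 months counts at its full length.*

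Counting the full interval matters. If only the part inside the window counted, a 7-month gap starting in the first 4 of the 24 months would leave at most 6 months inside and would pass (4/17 = 24% in the single-gap model). With full length counted, no gap of more than six months within the 24 passes, because only 24 − 19 = 5 months lie before the window. The 24-month span should not be shortened to 19.

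Reporting how many patients in each database enter through the fallback would show whether the point matters in practice.

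The cost is one sentence and a simple change to the cohort code. Some sparsely observed fallback patients are dropped, including some who were in fact enrolled throughout. The loss could be larger if the fallback is used at Ochsner or Partners, since section 5.2 says that their records do not hold every subsequent prescription.
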